2. OBJECTIVES AND OUTCOME MEASURES

2.1. Primary

Objective	Brief Description/Justification of Outcome Measure	Outcome Measured By	Time Frame
Evaluate ORR in patients receiving NKTR-214 in combination with palliative radiation, and pembrolizumab.	Response to anti-PD-1 therapy can be quite durable in patients with metastatic or recurrent HNSCC (~ 22 months); however, low ORR (~ 20 %) limits therapeutic benefit in this population as a whole. Improving ORR could result in a dramatic impact on survival of patients with metastatic or recurrent HNSCC.	ORR will include confirmed CR + confirmed PR and will be determined as per RECIST1.1. Progression of any radiated tumors will be considered in this evaluation but response of radiated tumor(s) will not be considered as evidence of response for the purpose of this study.	
 Pre-treatment standard-of-care imaging Standard-of-care imaging 3 to 6 months after Cycle 1

2.2. Secondary

Objective	Brief Description/Justification of Outcome Measure	Outcome Measured By	Time Frame
Evaluate the safety of NKTR-214 in combination with anti-PD-1 therapy and palliative radiation.	Grade 3 or grade 4 adverse event except those listed in 8.3.2 are anticipated to occur in < 25 % of patients based on the previous rate of 11 % with PD-1 inhibition and radiation. The safety of this combination must be established prior to evaluation of efficacy.	Toxicities \geq Grade 3 will be defined by the NCI Common Terminology Criteria for Adverse Events (CTCAE) v5. Toxicities not determined to be "unrelated" to treatment, will be considered treatment-related (including those that are unlikely, possibly, probably, or definitely related).	
 Study screening Cycle 1, day 1, 8 Cycle 2, day 1, 8 Cycle 3+, day 1 Every 4 months once off study without progression for 5 years, Every 6 months once off study with progression for 3 years

Objective	Brief Description/ Justification of Outcome Measure	Outcome Measured By	Time Frame
Determine CB, PFS, duration of response, and OS after treatment with NKTR-214, anti- PD-1, and palliative radiation.	PFS, OS, CB, and duration of response were chosen as efficacy outcomes based on prior immunotherapy trials. Duration of response is particularly important, as more durable responses are expected with immunotherapy.	
 CB will include confirmed complete response (CR) + confirmed partial response (PR) + stable disease at \geq 6 months (SD) and will be determined as per RECIST1.1. PFS is defined as the time from D1 of treatment until the criteria for disease progression is met as defined by RECIST1.1 or death as a result of any cause. OS is defined as time from D1 of treatment until death as a result of any cause. Duration of response is the period measured from the time that measurement criteria are met for complete or partial response (whichever status is recorded first) until the date that recurrent or progressive disease is objectively documented. 	
 D1 of treatment Standard-of-care imaging follow-up \sim3 and 6 months after Cycle 1 Time of disease progression Death
Determine the impact of NKTR-214, palliative RT, and anti-PD-1 therapy on patient-reported health-related quality of life (HRQoL)	In incurable diseases, patient reported outcomes and quality of life have great influence in a patients' choice of therapy.	
 Patient-reported HRQoL will be monitored to evaluate patient tolerance of treatment using EORTC QLQ-C30, EORTC QLQ-H&N35, and EQ-5D. HRQoL will be analyzed in subjects who received \geq 1 dose of study drug and have \geq 1 HRQoL assessment. 	
 Cycle 1, Day 1 pre-treatment Cycle 1, Day 8 Cycle 2, Day 8 Cycle 3, day 1 and every day 1 every 4 cycles (Q12 weeks) to discontinuation of therapy (Sect 5.5) 30 days post treatment

2.3. Tertiary/Exploratory

Objective	Brief Description/Justification of Outcome Measure	Outcome Measured By	Time Frame
Evaluate each subject's tumor expression of PD-L1 by histology and determine whether this predicts response to NKTR-214, palliative RT, and anti-PD-1 therapy.	PD-L1 expression has been shown to predict response to immunotherapy regimens. If PD-L1 expression correlates with outcome, it could be used in the future to select patients who have greatest benefit from this regimen.	• Expression of PD-L1 by histology	• Baseline • Cycle 2, Day 8
Evaluate the immunologic activation induced by NKTR-214, palliative RT, and anti-PD-1 using serologic and flow cytometry immune assays and T cell receptor sequencing.	Evaluation of the in vivo immune response will help better define the mechanism of action of this combination therapy.	• Levels of IFN- γ expressing and CD122+ T cells in Peripheral Blood Mononuclear Cells (PBMC) • Diversity and clonality of the T cell receptor repertoire by deep sequencing of PBMC	• Cycle 1, 2, and 3, Day 1 prior to treatment infusion • Cycle 1, 2, and 3, Day 8 • 30 days post-treatment
Evaluate for histological evidence of antitumor activity based on the cellular phenotype of infiltrate.	Evaluation of the in vivo immune response will help better define the mechanism of action of this combination therapy.	• Levels of tumor infiltrating lymphocytes by histology	• Baseline • Cycle 2, Day 8

3. STUDY DESIGN

This is a Phase II study to characterize the efficacy of NKTR-214 in combination with palliative radiation, and anti-PD1 in metastatic head and neck cancer patients. These patients very frequently require palliation of local symptoms with radiation in combination with systemic therapies and currently have very limited systemic options, making this an ideal population for investigation of NKTR-214 combination therapy. The study has been designed as a phase II due to the results of PIVOT-02, which demonstrate safety of anti-PD1 and NKTR-214 at the doses utilized in this study. The palliative radiation therapy delivered is unlikely to significantly increase toxicity. We will conduct efficacy evaluation on 24 participants. Under the null hypothesis for ORR ≤ 0.22 , based on one-sided one sample proportion test with type I error of 0.1, the expected power levels to detect alternative ORRs of 0.35, 0.4, and 0.45 are 55 %, 74 %, 87 % respectively. The null hypothesis will be rejected and superiority concluded if 8 or more responses are observed in 24 participants. This design yields a type I error rate of .04 and power of 0.8 when the true response rate is 44 %.

4. STUDY POPULATION

4.1. Participant Inclusion Criteria

To be eligible to participate in this study, an individual must meet all of the following criteria:

1. Written informed consent and HIPAA authorization for release of personal health information. NOTE: HIPAA authorization may be included in the informed consent or obtained separately
2. Qualify for anti-PD-1 therapy based on current guidelines at the time of registration. This includes the standard requirement for the participant's tumor to have been previously determined to express PD-L1 with a combined positive score ≥ 1 , as determined by an FDA-approved test.
3. Age 18 years and older at the time of consent
4. ECOG Performance Status of 0-2 within 30 days prior to enrollment
5. Histologically proven diagnosis of head and neck squamous cell carcinoma that is metastatic or recurrent disease that is surgically incurable
6. Prior cancer treatment other than anti-PD-1 therapy must be completed at least 30 days prior to registration and the subject must have recovered from all reversible acute toxic effects of the regimen (other than alopecia) to \leq Grade 1 or baseline. Patients may not undergo concurrent anti-cancer treatment during treatment with protocol therapies. This includes no treatment with growth factors, tyrosine kinase inhibitors, tumor-specific antibodies, or cytotoxic chemotherapies such as cisplatin. Patients who have previously or are currently taking an anti-PD-1 therapy are eligible for this study if they meet eligibility criteria 2. Patients who have previously taken any other immune checkpoint inhibitor are eligible as long as they have completed that treatment at least 30 days prior to registration and meet all other eligibility criteria.
7. Subjects with central nervous system (CNS) metastases are eligible if the CNS lesions are stable for at least 2 months and if tapered off treatment doses of systemic corticosteroids for at least 2 weeks prior to enrollment on the trial. Management with maintenance physiologic doses of corticosteroids (equivalent doses of prednisone ≤ 10 mg daily) is acceptable.
8. Subjects must have an "index" tumor that: 1) is deemed by the treating radiation oncologist to potentially benefit from palliative radiation 2) is amenable to biopsy, 3) is ≥ 1 cm in longest dimension.
9. Demonstrate adequate organ function as defined in the table below; all screening labs to be obtained within 30 days prior to enrollment

System	Laboratory Value
Hematological	
White blood cell (WBC)	$\geq 3,000/\text{mm}^3$
Absolute Neutrophil Count (ANC)	$\geq 1,500/\text{mm}^3$
Hemoglobin (Hgb)	$\geq 9 \text{ g/dL}$
Platelets	$\geq 100,000/\text{mm}^3$
Renal	
Serum creatinine	$\leq 2.0 \text{ mg/dL}$
Hepatic	

Total Bilirubin	$\leq 2.0 \times \text{ULN}$ (< 3.0 for subjects with Gilbert's Syndrome)
Aspartate aminotransferase (AST)	$\leq 3 \times \text{ULN}$
Alanine aminotransferase (ALT)	$\leq 3 \times \text{ULN}$

10. Females of childbearing potential must have a negative serum pregnancy test within 14 days prior to enrollment and must agree to use effective contraception during active treatment and for 5 months after last dose of pembrolizumab and/or NKTR-214. NOTE: Females are considered of childbearing potential unless they are surgically sterile (have undergone a hysterectomy, bilateral tubal ligation, or bilateral oophorectomy) or they are naturally postmenopausal for ≥ 12 consecutive months.
11. As determined by the enrolling physician or protocol designee, ability of the subject to understand and comply with study procedures for the entire length of the study

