5.8.1. Selection of an Index Tumor Site

From the tumor site(s) receiving palliative RT, a targeted (index) tumor will be selected at the discretion of the attending physician based on need for palliative radiation, ease of being able to obtain post-treatment biopsies from that site, and size at least 1 cm in longest dimension. Whenever possible, the targeted region should not have received RT prior to enrollment in this study. Palliative RT may be delivered to other sites of disease if deemed necessary and safe.

5.8.2. *Radiation Dose (SOC)*

The treating physician will use his/her discretion to decide between a dose and fractionation schedule of 8 Gy x 3 or 4 Gy x 5. Radiation can be delivered either daily or every other day and is generally provided on weekdays only. The treating physician will also use his/her discretion if multiple sites of disease will be treated with RT. If multiple sites of disease are being treated, these treatments should conclude between days -7 to -3 relative to the second doses of anti-PD-1 and NKTR-214.

5.8.3. *Radiotherapy Delivery (SOC)*

RT delivery will follow standard practice for palliative RT treatment and will utilize megavoltage (MV) photons or electrons. Any number or arrangement of beams may be used at the discretion of the treating physician to achieve target coverage and conformality.

Treatment Simulation, Subject Positioning and Set-up

Subject will be positioned in a comfortable position. Any immobilization apparatus may be used at the discretion of the treating physician as long as it does not interfere with the proper functioning of any necessary treatment planning or image-guidance systems. A CT simulation will be performed for all patients to facilitate treatment planning, consistent with standard practice approaches for the planning of palliative RT. The planning CT scan may be done with intravenous contrast if this is beneficial for target or normal tissue segmentation. CT scan thickness will be ≤ 0.3 cm. Planning CT scan will be acquired with the subject in the same position and using the same immobilization device as for treatment. At a minimum, all tissues within 5 cm of the target volume will be included in the CT scan. For spinal lesions treated with 8 Gy x 3, a pre-treatment MRI is required to assess the extent of disease and position of the cord. This must be fused with the planning CT scan.

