11.3. Final Analysis Plan

Any subject who receives at least one dose of NKTR-214 on this protocol will be evaluable for ORR. All subjects with measurable disease who have received at least one cycle of treatment and have their disease re-evaluated will be evaluable for assessment of objective response.

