11.3.1. Analysis Plans for Primary Objective

ORR will include confirmed complete response (CR) + confirmed partial response (PR) and will be assessed based on RECIST 1.1 criteria. ORR will be reported with the 95 % confidence interval (CI). Progression of any radiated tumors will be considered in this evaluation but response of radiated tumor(s) will not be considered as evidence of response for the purpose of this study unless all tumor sites are radiated.

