12.1.1. Malignant Lymph Nodes

To be considered pathologically enlarged and measurable, a lymph node must be ≥ 15 mm in short axis when assessed by CT scan (CT scan slice thickness recommended to be no greater than 5 mm). At baseline and in follow-up, only the short axis will be measured and followed.

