12.2. Non-measurable Lesions

All other lesions (or sites of disease), including small lesions (longest diameter < 10 mm or pathological lymph nodes with ≥ 10 to < 15 mm short axis), are considered non-measurable disease. Bone lesions, leptomeningeal disease, ascites, pleural/pericardial effusions, lymphangitis cutis/pulmonitis, inflammatory breast disease, and abdominal masses (not followed by CT or MRI), are considered as non-measurable.

NOTE: Cystic lesions that meet the criteria for radiographically defined simple cysts should not be considered as malignant lesions (neither measurable nor non-measurable) since they are, by definition, simple cysts. 'Cystic lesions' thought to represent cystic metastases can be considered as measurable lesions, if they meet the definition of measurability described above. However, if non-cystic lesions are present in the same subject, these are preferred for selection as target lesions.

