12.3. Target Lesions

All measurable lesions up to a maximum of 2 lesions per organ and 5 lesions in total, representative of all involved organs, should be identified as target lesions and recorded and measured at baseline. Target lesions should be selected on the basis of their size (lesions with the longest diameter), be representative of all involved organs, but in addition should be those that lend themselves to reproducible repeated measurements. It may be the case that, on occasion, the largest lesion does not lend itself to reproducible measurement in which circumstance the next largest lesion that can be measured reproducibly should be selected. A sum of the diameters (longest for non-nodal lesions, short axis for nodal lesions) for all target lesions will be calculated and reported as the baseline sum diameters. If lymph nodes are to be included in the sum, then only the short axis is added into the sum. The baseline sum diameters will be used as reference to further characterize any objective tumor regression in the

measurable dimension of the disease. Target lesions will not include radiated tumor sites for this study unless all tumor sites have been radiated.

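### Eligibility does not require a measurable lesion that can be a target lesion, so a patient who cannot show a partial response can be enrolled and counted in the ORR denominator

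*Combined protocol and SAP*

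**What the plan says.** **Entry.** Among the 11 inclusion and 17 exclusion criteria (4.1, 4.2), only criterion 8 sets a tumor size. The index tumor must be one that may benefit from palliative RT and "2) is amenable to biopsy, 3) is ≥ 1 cm in longest dimension". No criterion asks for RECIST-measurable disease or for a lesion outside the RT field.

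**The index tumor is irradiated.** Section 5.8.1: "From the tumor site(s) receiving palliative RT, a targeted (index) tumor will be selected at the discretion of the attending physician".

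**Target lesions.** Section 12.3: "Target lesions will not include radiated tumor sites for this study unless all tumor sites have been radiated".

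**Measurability.** For nodes, 12.1.1 states that "a lymph node must be ≥ 15 mm in short axis when assessed by CT scan". Section 12.2 lists as non-measurable, among others, "Bone lesions, leptomeningeal disease, ascites, pleural/pericardial effusions". Section 12.1 needs one measurable lesion for disease to be measurable and does not exclude irradiated lesions.

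**Response.** Section 12.5 defines PR as a fall of at least 30% in the target-lesion sum from baseline. Section 11.3.1 says that response of irradiated tumors "will not be considered as evidence of response for the purpose of this study unless all tumor sites are radiated". Section 2.1 states the same rule with no exception: "response of radiated tumor(s) will not be considered as evidence of response for the purpose of this study". The opening of section 12 also gives none.

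**Denominator.** The first sentence of 11.3: "Any subject who receives at least one dose of NKTR-214 on this protocol will be evaluable for ORR". Its second sentence limits evaluability for objective response to subjects with measurable disease who received at least one cycle and were re-evaluated. Section 12.8.1 takes the proportion of all subjects. The Protocol Summary refers to an efficacy-evaluable population that is not defined under that name elsewhere.

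**The concern.** The one lesion that eligibility guarantees is the one the primary endpoint normally refuses to use. Nothing guarantees a second, usable lesion. A patient without a permitted target lesion has no baseline sum, and without a baseline sum there is no PR. If such patients stay in the denominator of a 24-patient single-arm trial, the observed ORR understates the activity of the combination in patients whose response can be measured, and the chance of meeting the success rule falls. Analysis cannot restore the missing measurements once patients have been dosed.

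**Working it through.** **Step 1: trace two eligible patients through the text.**

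| | Patient A | Patient B |
|---|---|---|
| Disease | Measurable neck mass (irradiated index tumor) plus untreated bone metastases | A single node, 12 mm in short axis |
| Criterion 8 | Can be met | Can be met (longest dimension at least 12 mm) |
| Permitted target lesion | None: not all sites are irradiated, so 12.3 bars the mass; bone is non-measurable (12.2) | None: below 15 mm short axis (12.1.1), even if all sites are irradiated |
| PR under 12.5 | Not possible, no baseline sum | Not possible, no baseline sum |
| In denominator, 11.3 first sentence and 12.8.1 | Yes, once dosed | Yes, once dosed |
| In denominator, 11.3 second sentence | Yes, if re-evaluated: the irradiated mass is still measurable under 12.1 | No |

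The best-overall-response table in 12.7 has no row for a patient without target lesions, apart from the progression rows that accept any target-lesion status. Patient A is therefore a problem under either sentence of 11.3. Patient B is a problem for the ORR only under the first.

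**Step 2: the plan's own figures.** Section 11.2 gives 24 participants, a null ORR of 0.22, success at 8 or more responses, type I error 0.04, and power 0.80 at a true rate of 44%. With X ~ Binomial(24, p), the exact values are:

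- 8 or more: P(X ≥ 8) = 0.138 at p = 0.22 and 0.897 at p = 0.44.
- 9 or more: P(X ≥ 9) = 0.062 at p = 0.22 and 0.801 at p = 0.44.

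The stated error and power do not belong to the 8-response rule. That is a separate matter. It is noted here because it sets the m = 0 starting point at 0.897, not 0.80. Both cut-offs are shown below.

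**Step 3: illustrative effect.** Let m of the 24 be unable to respond, and let the rest respond with probability p. The number of responses is X ~ Binomial(24 − m, p). For the 8-response rule at p = 0.44:

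P(X ≥ 8) = 1 − Σ(j = 0 to 7) C(24 − m, j) × 0.44^j × 0.56^(24 − m − j)

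Expected ORR = 0.44 × (24 − m)/24; for m = 2 this is 0.44 × 22/24 = 0.403.

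| m | Expected ORR | P(8 or more), p = 0.44 | P(9 or more), p = 0.44 | P(8 or more), p = 0.22 |
|---|---|---|---|---|
| 0 | 44.0% | 0.897 | 0.801 | 0.138 |
| 2 | 40.3% | 0.825 | 0.691 | 0.090 |
| 4 | 36.7% | 0.718 | 0.550 | 0.054 |
| 6 | 33.0% | 0.575 | 0.389 | 0.028 |

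Two such patients cost 0.897 − 0.825 = 0.072 of power under the 8-response rule and 0.801 − 0.691 = 0.110 under a 9-response rule. The last column shows that the false-positive probability falls, not rises, as m grows.

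**Assumptions.** The documents give no value for m; 0 to 6 is an assumed range. The calculation takes 44% as the rate among patients who can be assessed. Section 11.2 does not say this. If 44% already describes all enrolled patients, P(8 or more) stays at 0.897.

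**The case against.** Four objections carry weight.

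1. **The denominator is not settled.** A reader might infer that every patient without a target lesion counts against the ORR once dosed. The documents do not support that for Patient B, who leaves the denominator if the second sentence of 11.3 governs. Nor does that sentence prove that the plan expects such patients to enrol; it may simply be the rule for handling them. The objection does not remove Patient A.

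2. **Unable to show a PR is not unable to respond.** A reader might call these patients structural non-responders. ORR includes CR, 12.6 defines CR for non-target lesions, and no section expressly bars a CR when there are no target lesions. The missing row in 12.7 is a gap, not a prohibition, and section 12 defers to the RECIST publication for detail. The power figures, which allow these patients no response of any kind, are therefore an upper bound on the loss for a given m.

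3. **The size is unknown.** m may be zero. Patient B is also an unusual case: the whole of an incurable recurrent or metastatic disease would be one small node that merits palliative RT. The point rests on Patient A.

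4. **The harm is limited.** The bias cannot create a false claim of efficacy, and these patients still contribute to safety, survival, quality of life and correlative objectives. It would be wrong to say that they contribute nothing to the trial.

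The all-sites-irradiated exception in 11.3.1 and 12.3 can help a patient with a measurable lesion whose every site is irradiated. It helps neither Patient A nor Patient B, and 2.1 and the opening of section 12 omit it.

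**Conclusion.** The concern holds in this form. Sections 4.1 and 4.2 admit patients with no lesion that 12.3 allows as a target. Such a patient cannot show a PR. Where the only measurable lesion is the irradiated index tumor and other untreated disease is non-measurable, the patient counts in the ORR denominator under both sentences of 11.3, provided that the second sentence's re-evaluation condition is met. Where no disease is measurable, the ORR is diluted only if the first sentence and 12.8.1 govern, so the two sentences must be reconciled.

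The direction is toward a lower ORR and lower power. The size is illustrative: for 2 to 6 affected patients, the chance of 8 or more responses falls from 0.897 to between 0.825 and 0.575. This rests on the assumed m, on no response at all in those patients, and on 44% applying to assessable patients only. The gap should be fixed, but the documents do not show that it will make the trial fail.

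**What to change.** 1. Add an inclusion criterion: at least one lesion, measurable under 12.1 or 12.1.1 at screening, that 12.3 permits as a target. This means a lesion outside the planned RT sites or, if all sites are to be irradiated and the sponsor keeps that exception, a measurable irradiated lesion.
2. Record the planned RT sites at screening, before target lesions are chosen, so that the criterion can be checked at registration.
3. Make sure the qualifying lesion has a baseline measurement by a method allowed in 12.1. Section 6.1 requires a CT of the neck but allows PET and/or chest CT elsewhere, with abdomen and pelvis CT optional, so a lesion below the neck may otherwise lack one.
4. Choose one ORR denominator in 11.3, align 12.8.1 and the Protocol Summary with it, and reconcile 2.1 and the opening of section 12 with 11.3.1 and 12.3 on the all-sites exception.

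The cost is a short amendment, a few more screen failures and slightly slower accrual. Most of the imaging is already scheduled; some patients may need a CT of a region that was otherwise optional. The criterion does not cover a target lesion irradiated later, which 5.8.3 allows after cycle 3; the response rules should say how that lesion is then assessed.
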